2.1 Risk / Benefit Assessment

Risk Versus Benefits to the Subjects

Risk levels are assessed on the severity level and the likelihood of occurrence. Both severity and occurrence levels for the risks assessed were considered low in this study.

Risk	Risk Level	Mitigation
Bio-incompatible – adverse reaction to the tympanic membrane	Low	Biocompatibility tests
Insufficient coverage of the TM perforation	Low	Range of Calcium alginate seal size available up to 5 mm
TM perforation does not fully repair / enlarges	Low	Results of Chinchilla study
Sclerosis of the TM	Low	Results of Chinchilla study
Granulation tissue remains resulting in delayed healing	Low	Results of Chinchilla study
Hemorrhage of TM	Low	Results of Chinchilla study
Hearing loss either poor or worsens	Low	Results of Chinchilla study
Lateral Displacement of Material	Low	Operative Technique indicates that larger flange is placed laterally.

The anticipated benefits of Tympanoseal are as follows:

1. Potential improvement in perforation repair rate indicated by chinchilla study.
2. Calcium alginate has been proven to increase fibroblast proliferation needed to produce collagen in the creation of a stable lamina propria layer. No current perforation seal repair material enables regeneration of the natural lamina propria.
3. Ease of application which will be similar to vent tube placement.
4. Calcium ions in the seal will exchange for sodium ions in exudates of the tympanic membrane wound potentially enhancing hemostasis and allowing collagen deposition to establish a stable lamina propria.
5. No risk of lateralization found in underlay techniques of tympanoplasty which may result in hearing loss and cholesteatoma.
6. No need for Gelfoam to be placed under the seal to support it and eliminates the risk of fibrosis in the middle ear reported with Gelfoam.
7. Supplying surgeons with an FDA approved device to act as scaffolding for tympanic membrane perforation repair. Currently all other products act as simple films and do not occlude a perforation.

The potential benefits described outweigh the low level of risk.

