8.6 Instructions for Use

Operative Technique

This technique description is the suggested treatment for the uncomplicated procedure. The preferred treatment is that which addresses the needs of the specific patient. The perforation site is evaluated under the operating microscope and the edges of the perforation are manipulated with a small pick so as to freshen the margins of the perforation.

A perforation sizing device will be provided with each device which will allow the surgeon to estimate the diameter of a hole in the tympanic membrane in order to choose a repair construct of appropriate size.

The lyophilized device is provided in a protective capsule with four sizes each attached to the other with progressively smaller flanges along its length. The capsule is opened by bending the lateral tabs on its larger bottom portion with one hand while carefully removing the smaller top portion with the other hand. The device can be easily extracted with forceps.

The proper size for a given perforation is excised with surgical scissors or scalpel. One flange will be of a larger diameter than the other; the surgeon will implant the device with the larger flange laterally. Insertion of Tympanoseal is similar to the placement of a tympanostomy tube. Immediately after insertion normal saline should be instilled in the external auditory canal to swell the device and completely occlude the perforation.

After Tympanoseal is in place, wax earplugs should be in place during showers and swimming.

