9.1.7 Adverse Events

Information regarding occurrence of adverse events will be captured from procedure date to study completion. Duration (start and stop dates), severity/grade, outcome, treatment and relation to study device will be recorded on the Adverse Event Tracking Log.

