10.2 Day of Procedure

1. Concomitant medications review.***
2. Perform abbreviated physical examination.***
3. Perform and record vital signs.***
4. Completion of Procedure and Device Information CRF.
5. Otomicroscopy with photograph of tympanic membrane after procedure with Tympanoseal in place.**
6. If applicable, record any Adverse Events.

**Note: See information below if enrollment and procedure are on the same day.

10.3 If Enrollment and Procedure are on the same day, the following tasks and CRFs are required to be completed.

1. Review the study with the subject (subject's legal guardian) and obtain written informed consent and HIPAA authorization and assent, if appropriate.
2. Assign the subject a unique screening number.
3. Record demographic data. (Enrollment / Demographics CRF)
4. Complete Eligibility Criteria CRF
5. Record general medical history and prior ENT history including the cause and size of perforation and length of time present, allergies, and other pertinent respiratory history. (Medical History (General) and ENT History CRF's)
6. Record concomitant medications. (Concomitant Medication CRF)
7. Perform physical examination, including vital signs. (Pre-Procedure Visit CRF)
8. Otomicroscopy with photograph of tympanic membrane **prior** to procedure.
9. Completion of Procedure and Device Information CRF.
10. Otomicroscopy with photograph of tympanic membrane **after** procedure with Tympanoseal in place.
12. If applicable, record any Adverse Events.

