11 ADVERSE EVENT REPORTING AND DOCUMENTATION

11.1 Adverse Events

An adverse event (AE) is any untoward medical occurrence in a clinical investigation of a medical device and that does not necessarily have a causal relationship with the treatment. An AE is therefore any unfavorable and unintended sign (including an abnormal laboratory finding), symptom or disease temporally associated with the administration of an investigational product, whether or not related to that investigational product.

The Investigator will determine with the subject, the occurrence of AEs during each subject visit and record the information in the site's source documents. Adverse events will be recorded in the patient CRF. Adverse events will be described by duration (start and stop dates and times), severity, outcome, treatment and relation to study device, or if unrelated, the cause.

AE Severity Grading

The guidelines below should be used to grade severity. It should be pointed out that the term "severe" is a measure of intensity and that a severe AE is not necessarily serious. (A 'severe' headache may not be a 'severe' AE.)

The collection period for all AEs will begin after device is implanted and ends at Subject Exit.

AE Severity Grading

Severity	Description
Mild (1)	Transient or mild discomfort; no limitation in activity; no medical intervention or therapy required. The subject may be aware of the sign or symptom but tolerates it reasonably well.
Moderate (2)	Mild to moderate limitation in activity, no or minimal medical intervention/therapy required.
Severe (3)	Marked limitation in activity, medical intervention/therapy required,, hospitalizations possible.
Life-threatening (4)	The subject is at risk of death due to the adverse experience as it occurred. This does not refer to an experience that hypothetically might have caused death if it were more severe.

AE Relationship to Study Device

The relationship of an AE to the study device should be assessed using the following the guidelines.

Relationship to Device	Comment
Definitely	Previously known toxicity of agent; or an event that follows a reasonable temporal sequence from use of the device; that follows a known or expected response pattern
Probably	An event that follows a reasonable temporal sequence from use of device; that follows a known or expected response pattern and that is unlikely to be explained by the known characteristics of the subject's clinical state or by other interventions.

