11.3 Serious Adverse Event Reporting

Study sites will document all SAEs that occur (whether or not related to study device). The collection period for all SAEs will begin after device is implanted and ends at Subject Exit.

In accordance with the standard operating procedures and policies of the local Institutional Review Board (IRB), the site investigator will report SAEs to the IRB within timeframe required. Please notify Grace Medical within 5 working days.

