APPENDIX 1 SCHEDULE OF STUDY VISITS

	Enrollment*	Procedure*	Same Day Enrollment & Procedure	4 Weeks (± 7 days)	10 Weeks (± 7 days)	16 Weeks (± 14 days)	Add'l Visit(s) 20 weeks, 24 weeks, 30 weeks 36 weeks (± 14 days)
Informed Consent	X		X				
Inclusion / Exclusion	X		X				
Medical /ENT History	X		X				
Physical Exam	X*	X*	X	X	X	X	X
Vital Signs	X*	X*	X	X	X	X	X
Study Visit Evaluation	X*	X*	X	X***	X***	X***	X***
Otomicroscopy with Photograph	X**	X**	PRE & POST	X	X	X	X
Use of Study Device		X	X				
Concomitant Medication	X*	X*	X	X	X	X	X
Adverse Event****		X	X	X	X	X	X
Subject Study Exit				X***	X***	X***	X***

*Enrollment and Procedure may be the same visit and duplicate CRFs do not need to be completed. Informed Consent must be signed prior to any study procedures.

** Otomicroscopy with Photograph is required Pre and Post Procedure.

*** If healing is noted by investigator, the subject may exit the study.

**** If applicable

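### The protocol gives two start points for adverse event collection, and the later one leaves out harm during the placement attempt

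*Protocol*

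**What the plan says.** Three sections of the protocol set the collection window:

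- Section 9.1.7: "Information regarding occurrence of adverse events will be captured from procedure date to study completion".
- Section 11.1: "The collection period for all AEs will begin after device is implanted and ends at Subject Exit".
- Section 11.3: "The collection period for all SAEs will begin after device is implanted and ends at Subject Exit".

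Other places touch on the point without settling it. The procedure-day list in Section 10.2 says "If applicable, record any Adverse Events" as its last item, and the same-day list in Section 10.3 ends in the same way. Appendix 1 marks its "Adverse Event" row in the procedure columns, with a footnote that says only that it applies where applicable. The definition in Section 11.1 opens with "any untoward medical occurrence in a clinical investigation of a medical device", which sets no lower time limit. Section 16.5, item 4, obliges the investigator to report to the sponsor any AE arising in the course of the study.

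**The concern.** The two start rules cannot both hold. The later one excludes a period in which the subject is already undergoing study surgery. Section 8.6 describes work on the membrane before the device is in place: "the edges of the perforation are manipulated with a small pick so as to freshen the margins of the perforation", then sizing and insertion. The risk table in Section 2.1 lists "Hemorrhage of TM" and enlargement of the perforation, both of which could plausibly follow from that work.

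Two consequences are possible. First, an event before implantation is complete may never reach the log, and a subject whose placement is attempted and abandoned may contribute no events at all. Second, the two sites may follow different sections, so that their rows in the pooled table cover different windows. Safety is the primary objective (Section 3.1), and the planned output is the number of patients with each event, its rate, severity and relationship to the device (Section 14). An event that was never recorded cannot be recovered at analysis.

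**Working it through.** The protocol states no figure that depends on this point, so there is none to reproduce. The check is a comparison of text, followed by an illustration of size.

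**Comparison of the windows**

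| Situation | Section 9.1.7 | Sections 11.1 and 11.3 |
|---|---|---|
| Harm on procedure day during margin freshening, sizing or insertion | Counted | Before the window opens |
| Harm in a subject whose placement is attempted but fails | Counted | The window never opens |
| Harm arising after implantation, up to exit | Counted | Counted |

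Sections 10.2 and 10.3 and Appendix 1 place AE recording on procedure day but give no start time. In both lists the item follows placement of the device and the post-placement photograph, which fits either rule. Section 11.1 asks for start and stop times as well as dates, so a site following it literally could separate events within the day and leave out those before implantation.

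**Size of one uncounted event**

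Inputs: 2 sites with up to 15 subjects each (Section 4), so 2 × 15 = 30. The single event is assumed for illustration. The intervals are exact (Clopper-Pearson) 95% limits. For x events in n subjects, the lower limit is the 2.5% quantile of Beta(x, n − x + 1), or 0 when x = 0. The upper limit is the 97.5% quantile of Beta(x + 1, n − x). For x = 0 the upper limit reduces to 1 − 0.025^(1/n).

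| Row | Rate | 95% CI |
|---|---|---|
| 1/30, event logged | 3.33% | 0.08 to 17.22% |
| 0/30, event not logged | 0% | 0 to 11.57% |
| 0/29, event not logged and the subject dropped from the denominator | 0% | 0 to 11.94% |
| 1/15, one site, event logged | 6.67% | 0.17 to 31.95% |
| 0/15, one site, event not logged | 0% | 0 to 21.80% |

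The 0/29 row is hypothetical: the protocol does not say what happens to the denominator after a failed placement.

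**How often it could arise**

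The protocol gives no rate of events before implantation. For an assumed per-subject risk p, the chance of at least one such event in 30 subjects is 1 − (1 − p)^30:

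- p = 2%: 1 − 0.98^30 = 45%
- p = 5%: 1 − 0.95^30 = 79%
- p = 10%: 1 − 0.90^30 = 96%

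These values show sensitivity to the assumption. They are not estimates.

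**The case against.** The strongest reply is that the gap is narrow and the stated question lies mostly after it. Both starts normally fall on the same calendar day, and from implantation to exit the rules agree. The primary objective concerns safety while the device serves as a scaffold during healing, and the synopsis's secondary objective concerns events while material is on the membrane. Bleeding from margin freshening precedes contact with the device. The second sentence of the AE definition also ties events in time to administration of the product. In addition, the general reporting duty in Section 16.5, AE recording at the procedure visit, the photographs before and after placement, and AE training at site initiation (Section 15.3.1) all make it less likely that an event is lost.

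Much of this stands as a limit on size. The affected period is short, bleeding or enlargement may still be visible on the post-placement photograph, and divergence between the sites is a possibility, not something the protocol shows. The arithmetic for one event is the same for any single missed event in 30 subjects.

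It does not remove the conflict. If the safety question is meant to start after implantation, Section 9.1.7 is wrong; if not, Sections 11.1 and 11.3 are. Insertion is itself part of device use, yet it also comes before the Section 11 start. The broad duty in Section 16.5 is a further statement at odds with Section 11, and nothing ranks the two. Site training could settle a convention, but the protocol gives the trainer two. The first interim monitoring visit normally comes only after most subjects at a site have had the four-week visit (Section 15.3.2), so early correction is not assured.

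A final objection is that the denominator of the AE table is commonly left to an analysis plan. That is fair for the tabulation wording. It does not apply to the collection window, which sites apply as events happen.

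**Conclusion.** The concern holds. The current text contains two incompatible start points for AE collection, and the one in the safety-reporting sections can undercount harm in a study whose primary objective is safety. It should be corrected, although it does not undermine the study as a whole.

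The direct effect is confined to events before implantation is complete and to failed placements. Within that limit, one unlogged event is enough to turn a 3.3% row into a 0% row and to lower the upper confidence limit from 17.2% to 11.6% at the full 30 subjects. This rests on a literal reading of Sections 11.1 and 11.3 and on at least one such event occurring, for which the protocol gives no rate. The contradiction itself needs no assumption.

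**What to change.** Reconcile Sections 9.1.7, 11.1 and 11.3 to a single start point. Suitable wording would be: *AEs and SAEs are collected from the start of the study procedure, whether or not the device is successfully placed, until the subject exits the study.* Refer to that sentence in the procedure-day AE items of Sections 10.2 and 10.3 and in the AE footnote of Appendix 1. In Section 14, or in the analysis plan if there is one, state that AEs are tabulated over all subjects in whom placement was attempted.

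The cost is one sentence aligned in three sections, cross-references in the visit lists and Appendix 1, and one phrase on tabulation. Sites may make a few extra log entries, and the reported AE rate may rise slightly, partly because of surgical manipulation and not the alginate. The device-relationship scale in Section 11.1, which already asks for the cause of unrelated events, can separate the two.

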LVG Pronova™ Sodium Alginate (30 mPas viscosity)	Acute systemic toxicity by intraperitoneal route rat	NovaMatrix Drug Master File 14993	No mortality or abnormal clinical signs with normal weight gain
LVG Pronova™ Sodium Alginate 3.5 mPas viscosity)	Acute systemic toxicity by intraperitoneal route rat	NovaMatrix Drug Master File 14993	No mortality or abnormal clinical signs with normal weight gain
LVG Pronova™ Sodium Alginate	Hemolysis	NovaMatrix Drug Master File 14993	No lysis of blood cells recorded
LVG Pronova™ Sodium Alginate	Implantation in rabbits	NovaMatrix Drug Master File 14993	Moderate inflammatory responses with no implant material remaining at site of implantation. Slightly greater tissue reaction was observed than at the sham operation site.
LVG Pronova™ Calcium Alginate	Cytotoxicity based on in vitro cell culture of 3T3 mouse fibroblasts	NovaMatrix Drug Master File 20497	Material had no cytotoxic effects on either cell lines

	and V79 Chinese hamster		
LVG Pronova™ Calcium Alginate	Acute systemic toxicity rats, s.c.	NovaMatrix Drug Master File 20497	No evidence of toxicity
LVG Pronova™ Calcium Alginate	Acute systemic toxicity rats, i.m.	NovaMatrix Drug Master File 20497	No evidence of toxicity
LVG Pronova™ Calcium Alginate	Subchronic toxicity Sprague Dawley rats, Charles River Laboratory	NovaMatrix Drug Master File 20497	No signs of toxic effects and no weight loss over study period
LVG Pronova™ Calcium Alginate	LD50 i.p. in rats	NovaMatrix Drug Master File 20497	1,407 mg/kg lethal dose in rats
LVG Pronova™ Calcium Alginate	LD50 i.v. in rats	NovaMatrix Drug Master File 20497	64 mg/kg lethal dose in rats
LVG Pronova™ Calcium Alginate	Rat implantation, dorsal left scapula of calcium alginate slurry in normal saline	NovaMatrix Drug Master File 20497	No signs of systemic toxicity, granulomas in two animals, foreign body reaction shortly after implantation
NovaMatrix self gelling sodium/calcium alginate gel	Rat implantation, dorsal right scapula and hindlimb of self gelling sodium/calcium alginate in normal saline	NovaMatrix Drug Master File 20497	No adverse systemic signs, no weight change and gelatinous thickening at the injection site days 3, 15, 31 and 60.
NovaMatrix self gelling sodium/calcium alginate gel	Rat subcutaneous injection	NovaMatrix Drug Master File 20497	No adverse toxic effects recorded, day 3 revealed cell infiltration, days 15 and 60 foreign body reaction

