NovaMatrix self gelling sodium/calcium alginate gel	Rat intramuscular injection	NovaMatrix Drug Master File 20497	No adverse toxic effects recorded, day 3 revealed cell infiltration, days 15 and 60 foreign body reaction
NovaMatrix self gelling sodium/calcium alginate gel, as manufactured for Grace Medical	ISO MEM elution using L-929 mouse fibroblast cells	WuXi Apptec report to Grace Medical, Inc.	Test article is not considered cytotoxic according to the conditions of this test.
NovaMatrix self gelling sodium/calcium alginate gel, as manufactured for Grace Medical	ISO intracutaneous irritation test	WuXi Apptec report to Grace Medical, Inc.	Score of 1 according to ISO protocols, was not irritating

NovaMatrix self gelling sodium/calcium alginate gel, as manufactured for Grace Medical	ISO Guinea pig maximization sensitization test, 2 extracts	WuXi Apptec report to Grace Medical, Inc.	Under the conditions of this protocol the test article did not elicit a sensitization response.
NovaMatrix self gelling sodium/calcium alginate gel, as manufactured for Grace Medical	ISO In vivo mouse micronucleus assay	WuXi Apptec report to Grace Medical, Inc.	The test article is considered non-mutagenic in this test system.
NovaMatrix self gelling sodium/calcium alginate	ISO mouse lymphoma with extended treatment	WuXi Apptec report to Grace Medical, Inc.	Test article was found to be non-mutagenic (non-genotoxic and non-clastogenic)
NovaMatrix self gelling sodium/calcium alginate	ASTM Hemolysis Assay-Direct Contact and Extraction Method	WuXi Apptec report to Grace Medical, Inc.	Test material was not hemolytic
NovaMatrix self gelling sodium/calcium alginate	Complement Activation C3a and SC5b-9	WuXi Apptec report to Grace Medical, Inc.	Test article did not activate complement more than control
NovaMatrix self gelling sodium/calcium alginate	ISO In Vivo Mouse Micronucleus Assay	WuXi Apptec report to Grace Medical, Inc.	Test article was not genotoxic
NovaMatrix self gelling sodium/calcium alginate	ISO Bacterial Mutagenicity Test-Ames Assay	WuXi Apptec report to Grace Medical, Inc.	Test article was not mutagenic

Ototoxicity testing of calcium alginate samples using Grace Medical's proprietary method was performed by [name] and [name] of the University of Kansas Medical Center. The Auditory & Vestibular Neuroscience Lab tested the ototoxicity by using an in- mouse model when exposed to Grace Medical's alginate formulation via surgical implantation.

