1.2 Overview of Clinical Studies

Adverse Events Associated with NovaMatrix Self Gelling Alginate

Clinical trials of Algisyl (Lone Star Heart, Laguna Hills, CA) a cardiac repair gel made with NovaMatrix self gelling alginate have demonstrated adverse events in 21.4% of test subjects. None of these events have been related to alginate itself but to development of infections or worsening of heart conditions. No other occurrences of adverse events from use of NovaMatrix self gelling alginate have been found.

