Possibly	An event that follows a reasonable temporal sequence from use of the device; that follows a known or expected response; but that could readily have been produced by a number of other factors.
Unrelated	An event that can be determined with certainty to have no relationship to the study device.

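### The relationship table in Section 11.1 has no level for a well-timed but unexpected adverse event of uncertain cause, and as printed its top level contains the two below it

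*Protocol*

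**What the plan says.** The relationship table in Section 11.1 of the protocol has four rows.

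- *Definitely*: an already known toxicity of the agent, "or an event that follows a reasonable temporal sequence from use of the device; that follows a known or expected response pattern". The printed cell ends there, without a full stop.
- *Probably*: the same timing and response conditions, with the addition "that is unlikely to be explained by the known characteristics of the subject's clinical state or by other interventions".
- *Possibly*: a well-timed event "that follows a known or expected response; but that could readily have been produced by a number of other factors".
- The last row, *Unrelated*, sets certainty as its only condition: "An event that can be determined with certainty to have no relationship to the study device".

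There is no row for an unlikely or unassessable relationship. The table is introduced as guidelines that should be used for the assessment. The text before it asks sites to record "relation to study device, or if unrelated, the cause". Section 9.1.7 places the rating on the Adverse Event Tracking Log. Section 14 plans no statistical analysis; it promises tables for the FDA that include each event's relationship to the device. Section 3.1 makes safety the primary objective, and under Section 8 every subject receives the device.

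**The concern.** A causality scale should give each event one level, with the evidence required rising towards the top. This table appears to miss on both counts.

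First, every related level depends on the response being known or expected (or on a known toxicity), while the only other level demands certainty. An unexpected event is one that an early device study should be able to label, yet it has no level unless it is certainly unrelated.

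Second, the top row as printed says nothing about other causes, whereas the two rows below it do. The highest level is then the easiest to meet.

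There is no control group, so the relationship rating is the planned means of separating device effects from background events. Two sites applying these rows could label the same event differently, and both could be following the text.

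**Working it through.** No figure in the protocol is at issue, so the check is a logical one on the four definitions.

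**Inputs (Section 11.1).** X = known toxicity; T = reasonable timing; K = known or expected response; A = other causes, graded as excluded, unlikely, in between, or readily explaining the event; C = certainly unrelated. The grades of A are an assumption made for this check.

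**Printed rules.**

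- *Definitely* = X, or (T and K)
- *Probably* = T and K and A in {excluded, unlikely}
- *Possibly* = T and K and A = readily
- *Unrelated* = C

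**Step 1: well-timed events that are neither a known toxicity nor certainly unrelated (T = 1, X = 0, C = 0).** There are 2 × 4 = 8 combinations of K and A.

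| Other causes | Known or expected response | No known or expected response |
|---|---|---|
| Excluded | *Definitely* and *Probably* | none |
| Unlikely | *Definitely* and *Probably* | none |
| In between | *Definitely* only | none |
| Readily explain | *Definitely* and *Possibly* | none |

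Three combinations fit two levels, one fits one level, and four fit none. The right-hand column is the gap. It does not depend on how the *Definitely* cell ends, because a further clause there could only make that level harder to meet.

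**Step 2: nesting.** *Probably* and *Possibly* each contain (T and K), and (T and K) is by itself enough for *Definitely*. Whatever the values of X, A and C, an event that meets either lower level also meets the top one. This step does depend on the cell being complete as printed.

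**Step 3: is the gap empty in practice?** The protocol does not define a known or expected response. The following may reasonably count:

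- the animal tissue reactions in Section 1.1, such as "granulomas in two animals, foreign body reaction shortly after implantation" and "day 3 revealed cell infiltration, days 15 and 60 foreign body reaction";
- the eight risks in Section 2.1, one of them a broad adverse reaction of the tympanic membrane;
- microbial colonization and diminished hearing in Section 3.2.

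That covers much of what one would anticipate. It does not cover everything: new tinnitus, for example, is in none of these lists. The human experience cited in Section 1.2 is with a cardiac gel and adds no expected response: "None of these events have been related to alginate itself but to development of infections or worsening of heart conditions".

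**Step 4: size per subject.** At the maximum of 30 subjects, one subject's event rated *Definitely* instead of *Probably* moves each of those two rates by 1/30 = 3.3 points (1/15 = 6.7 points at one site). It moves the pooled related rate by 0. An event in the gap moves the pooled related rate by 0 if it is put in *Possibly*, and by 1/30 only if it is called *Unrelated* without the required certainty.

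**The case against.** Several counter-arguments have force.

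- *The overlap may come from reading the PDF.* The *Definitely* cell alone lacks a full stop, and the *Probably* row continues after the same words. A lost clause is plausible. This stands, so the overlap is conditional on a check of the original. The gap is not.
- *Events without reasonable timing.* These also lack a level, and adding their 8 combinations to the 4 above gives 12 of 16. A reader might infer that most events cannot be rated. The documents do not support that: the adverse-event definition in Section 11.1 already requires a temporal association, which removes at least some of the 8. The counts are also logical combinations that depend on the grid chosen, not event frequencies. The well-timed cells are the core.
- *Expectedness is elastic.* The phrase is not limited to the protocol's own lists, and Section 8.6 likens insertion to placing a tympanostomy tube, so an investigator could draw on that experience. This narrows the gap but does not close it.
- *These are guidelines.* Judgement is allowed, but the text does not tell two raters which of two satisfied rows to choose, or what to do when none is satisfied.
- *Unrelated and the named cause.* A reader might infer that a named cause is part of the *Unrelated* definition and so keeps doubtful events out. The definition asks for certainty only; the cause is an item to record once the rating is made.

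**Conclusion.** The point holds, at minor to moderate weight. The gap for well-timed, unexpected events of uncertain relation follows from the printed definitions. The nesting of *Probably* and *Possibly* inside *Definitely* also follows, provided the original cell carries no further clause.

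The damage is limited to the relationship label. A reader might infer that safety events would be missed. The documents do not support that: adverse events are recorded whatever their rating, serious events are documented whether or not related (Section 11.3), and unanticipated effects and problems have their own reporting rules (Sections 11.4 and 16.5). A reader might also infer that the related-event rate will be wrong. The overlap cannot change the pooled count. For the gap, the certainty rule makes *Possibly* a natural default, so an error in the pooled rate is possible but not shown to be likely. What is unreliable is the split among the related levels, and the placing of the few events that meet no definition.

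**What to change.** First compare the *Definitely* row with the original document. Then amend the one table in Section 11.1:

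1. Rate *Unrelated* first, with its certainty requirement unchanged, and apply the other levels only to events that are not certainly unrelated. Without this order, a well-timed event certainly due to something else would meet both *Possibly* and *Unrelated*.
2. Delete the known-or-expected-response condition from *Probably* and *Possibly*. *Probably* becomes reasonable timing, other causes unlikely, *Definitely* not met. *Possibly* becomes any other well-timed event that meets neither level above it.
3. If the original row has no such clause, add to *Definitely* that no other cause plausibly explains the event, and apply this to the known-toxicity limb as well.
4. State in one line where the remaining events without reasonable timing go. A fifth level is optional.

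Check: under rules 1 to 3 the eight well-timed combinations above fall once each, 1 in *Definitely*, 3 in *Probably* and 4 in *Possibly*. Across all 32 combinations with C = 0 the split is 5 *Definitely*, 5 *Probably*, 8 *Possibly* and 14 left to the line in item 4 (5 + 5 + 8 + 14 = 32). Of those 14, 6 involve a known toxicity without reasonable timing where another cause is not excluded. The printed table calls these *Definitely*, so the line should name them explicitly.

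Cost: one table and the relationship key on the log, with no new data or visits; prior written IRB approval of the amendment (Section 16.1) at two sites; and re-rating of any events already rated. Fewer events may qualify as *Definitely*, and the related-event rate may come out slightly higher, because unexpected events would now have a related level to go to.
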